4.3 Exploratory Endpoints and Assessment Methods

As with the primary and secondary objectives, for each of the exploratory outcomes below, we will only count the first event of the outcome per season and censor after the first event.

For any of the exploratory endpoints below, interpretation of any findings will be challenging. If a significant rVE is found, we will not be able to rule out various sources of confounding as alternative explanations (as opposed to the interpretation that this is the true rVE against any outcome). Any exploratory findings should be interpreted with caution.

- To estimate the rVE of Flublok Quadrivalent vaccine versus SD-IIV in vaccinees aged 50–64 years against the following exploratory outcomes if time allows:

- a. Diagnosed with influenza

We will consider for inclusion in the analysis adults aged 50–64 years who were (1) found to be PCR-positive for influenza and (2) clinically-diagnosed with influenza using ICD-10 codes, such as J09*, J10*, or J11* in any setting, and were untested. Additional ICD-10 codes may be considered upon review of relevant diagnoses. This outcome will exclude those with a clinically-diagnosed influenza but are tested and PCR-negative.

The diagnosis must occur during the influenza season and no later than 14 days after the last day of the influenza season, as determined by KPNC.

- b. All-cause hospitalizations

We will consider for inclusion in the analysis adults aged 50–64 years who were hospitalized. Hospitalizations following a scheduled elective surgery or similar may be excluded. The hospitalization must occur during the influenza season and no later than 14 days after the last day of the influenza season, as determined by KPNC.

- c. All-cause mortality

We will consider for inclusion in the analysis adults aged 50–64 years who died for any reason. The death must occur during the influenza season and no later than 14 days after the last day of the influenza season, as determined by KPNC.

- To estimate the rVE of Flublok Quadrivalent vaccine versus SD-IIV in other age ranges of vaccinees — aged 18–64 years and aged 18–49 years — against the following outcomes if time allows:

- a. All PCR-confirmed influenza

- b. All PCR-confirmed influenza A and influenza B (separately)
- c. PCR-confirmed hospitalized influenza
- d. Hospitalized CAP
- e. Hospitalized cardio-respiratory events combined
- f. All-cause hospitalization (excluding pregnancy-related hospitalizations)
- g. All-cause mortality

- Sub-analyses of the primary and secondary outcomes of sub-groups defined by pre-existing conditions (as described in Sections 2.2 and 4.2) will be conducted among adults 18–49 years as feasible
- To estimate the rVE of Flublok Quadrivalent vaccine versus SD-IIV among adults aged 18–64 years for PCR-confirmed influenza A subtypes (A(H1N1)pdm09 and A(H3)) and lineage for type B influenza (B/Victoria, B/Yamagata) as feasible

For at least the first influenza season (2018–2019) and potentially another season, we will subtype a proportion of PCR positive outpatient specimens from adults aged 18–64 years.

We will prioritize subtyping of adults aged 18–64 years who were vaccinated with Flublok or SD-IIV. After subtyping those specimens, we will then prioritize subtyping a fraction of unvaccinated cases by time interval to ensure we have subtyping data throughout the season. We will create time intervals from which to randomly sample unvaccinated adults (e.g., weeks with higher incidence of influenza at the peak of the season may be broken down into 1-week intervals, while lower incidence weeks may be 2-week intervals). We will prioritize sampling unvaccinated adults aged 50–64 years (primary analysis age group), followed by aged 18–49 years, resources permitting.

The data on subtypes from vaccinated and unvaccinated PCR-positive adults will be used to determine what strains were circulating at any point during the influenza season. This subtype data will then be used to impute what the subtype likely would have been for those adults who were found to be PCR-positive for influenza, but for which no subtype data are available. For example, if at the peak of our influenza season, we find that 90% of influenza A cases are H1N1, we would assume that this proportion of PCR positive influenza A cases (for which we do not have subtype data) from that time period were also H1N1.

Because we will have subtype data by calendar date, if there is a change in the predominant circulating strain at some point in the influenza season, we may be able to determine whether rVE also changes with the shift in subtype.

We may describe the proportion of influenza subtypes in unvaccinated versus vaccinated adults. The unvaccinated adults will serve as a comparison group for descriptive purposes.

For the above outcomes for the additional age groups aged 18–64 years and 18–49 years, we will use the same assessment methods as described in Sections 4.1, 4.2, and 4.3.

5 Statistical Methods and Determination of Sample Size

The statistical analyses will be performed under the responsibility of KPVSC using SAS® Version 9.4 software or later. The results of the statistical analysis will be available in the final study report.

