5.1.1.2 Statistical Methods

The primary, secondary, and exploratory analyses will use Cox regression on a calendar timeline to obtain an adjusted estimate of the relative hazard ratio (rHR) for each outcome, adjusted for age, sex, race/ethnicity, and facility or service area. The null hypothesis (that the $\log rHR = 0$) will be tested using the Wald test (based on the ratio of the adjusted $\log rHR$ estimate to its corresponding standard error estimate). The following covariates have been selected *a priori* to include in our model (via the propensity score, described further below):

- Age at time of vaccination (continuous)
- Sex
- Race (some small categories may be combined, if necessary):
 - White
 - Black
 - Asian
 - Pacific Islander
 - Native American
 - Multiracial
 - Unknown/Other
- Ethnicity:

- Hispanic
- Non-Hispanic/Unknown
- KPNC Facility or Service Area

In addition to estimating the rHR, conditional on the covariates above, we will consider whether the rVE of Flublok varies across subgroups or over time. For example, we may examine whether the rHR varies with:

- Time-since-vaccination: number of days, counting from Day 15 after vaccination (where day 0 is the day of vaccination)
- Time-since-beginning-of-the-season
- Season: Year 1, Year 2, or Year 3
- Comorbidities: Diagnostic cost groups (DxCG) risk scores from the ICD-based proprietary risk adjustment and predictive modeling system may be used. DxCG calculates projected healthcare costs for each member for the upcoming year based on demographics, diagnoses, costs, and utilization in the previous year. It may also be included as a proxy for overall health status of the individual.
- Prior healthcare utilization (e.g., number of emergency department visits or hospitalizations in prior year, outpatient visits in prior year)
- Influenza vaccine type received (or none) during the previous year

Adults who are included in our analysis must receive either Flublok or an SD-IIV. The majority of influenza vaccinations are administered in the KPNC region by the end of calendar year. It is possible that Flublok will not last until the end of the influenza season, which is typically in the spring of the following year, as determined by KPNC. Based on our alternating weekly schedule—one week of Flublok followed by one week of an SD-IIV—weeks are “paired” for balance.

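### Exploratory subtype rVE: untyped cases are filled in from a strain mix that ignores vaccine received; if those cases enter the Cox models, real differences between subtypes are understated

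*SAP*

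**What the plan says.** SAP 4.3 sets rVE by A subtype and B lineage in adults 18–64 as an exploratory objective, to be done as feasible. The typing plan follows under the same bullet:

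- **Seasons.** "For at least the first influenza season (2018–2019) and potentially another season".
- **Specimens.** "we will subtype a proportion of PCR positive outpatient specimens from adults aged 18–64 years". The proportion is not given, and inpatient specimens are not mentioned.
- **Order.** "We will prioritize subtyping of adults aged 18–64 years who were vaccinated with Flublok or SD-IIV"; a sample of unvaccinated cases, drawn by period, comes only afterwards.
- **Strain mix.** "The data on subtypes from vaccinated and unvaccinated PCR-positive adults will be used to determine what strains were circulating" at each point in the season.
- **Imputation.** The mix is used to assign a likely subtype to PCR-positive adults without one. The worked example takes a period in which 90% of typed influenza A cases are H1N1; then "we would assume that this proportion of PCR positive influenza A cases (for which we do not have subtype data) from that time period" are treated as H1N1 too.

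The conditioning described is virus type and time period only. On the analysis side, SAP 5.1.1.2 says "The primary, secondary, and exploratory analyses will use Cox regression on a calendar timeline". Later in that section, at the end of the paragraph on membership, it states that missing data are not to be imputed. Nothing links that sentence to the subtype rule in 4.3.

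**The concern.** If the two vaccines protect differently against H1N1 and H3, the strain mix among breakthrough cases differs between the arms. A single mix applied to both arms removes that difference from every untyped case. A subtype with no benefit is then credited with some, and a subtype with real benefit is diluted. The contrast that this objective exists to estimate shrinks.

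The general caution in SAP 4.3 ("Any exploratory findings should be interpreted with caution") is tied to confounding. A reader would not learn from it that the imputation step can itself draw the subtype estimates together.

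**Working it through.** **Inputs.** The documents give no figure for subtype rVE, so there is none to reproduce. From the protocol: 400,000 vaccinees per arm per season and a comparator rate of 0.00218 for test-positive influenza at ages 18–64 (power appendix), i.e. 400,000 × 0.00218 = 872 SD-IIV cases per season. From the SAP: the 90% H1N1 example. Assumed: true subtype rVEs, typed shares, and typing that is random within arm and period.

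**Formula.** Let c1 and c3 be the H1N1 and H3 shares of SD-IIV cases, r1 and r3 the true rate ratios, and R = c1·r1 + c3·r3 the overall ratio. Let f be the typed share in both arms and p the pooled H1N1 share among typed cases. After imputation,

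rHR(H1N1) = [f·c1·r1 + (1−f)·p·R] / [f·c1 + (1−f)·p],

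and likewise for H3 with c3, r3 and 1−p. Each is a weighted average of the true subtype ratio and R. With equal typed shares, each subtype rVE therefore moves toward the overall rVE, whatever p is. There is no bias if f = 1 or r1 = r3.

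**Worked case: truth 0% / 30%, 50:50 mix, 80% typed, per 100 SD-IIV cases.**

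- True cases (H1N1/H3): SD-IIV 50/50; Flublok 50/35.
- Typed: SD-IIV 40/40; Flublok 40/28. Pooled p = 80/148 = 0.5405.
- Untyped: SD-IIV 20, assigned 10.81/9.19; Flublok 17, assigned 9.19/7.81.
- Completed: SD-IIV 50.81/49.19; Flublok 49.19/35.81.
- rVE: H1N1 1 − 49.19/50.81 = 3.2%; H3 1 − 35.81/49.19 = 27.2%.

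**Other typed shares (estimated rVE, H1N1 / H3).**

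| Assumed truth and mix | 95% typed | 90% | 80% | 50% |
|---|---|---|---|---|
| 0% / 30%, 50:50 | 0.8 / 29.3 | 1.6 / 28.6 | 3.2 / 27.2 | 7.8 / 22.8 |
| 10% / 30%, 50:50 | – | 11.0 / 29.1 | 12.1 / 28.1 | 15.1 / 25.1 |
| 0% / 30%, 90:10 (H3 only) | – | 27.6 | 25.2 | – |

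With the SAP's 90:10 example mix, the minority subtype is off by 30 − 25.2 = 4.8 points at 80% typed. If strains separate in time (90:10, then 10:90), the period-specific mix helps: at 80% typed the estimates are 1.2% / 29.0%. If all cases were untyped and given a borrowed 50:50 mix, both would read 1 − 0.85 = 15%.

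**Coverage of a nominal 95% interval.** Simulation with 20,000 runs, 872 SD-IIV cases in one season all taken as influenza A, truth 0% / 30%, 50:50 mix: 94–95% at 90% typed, 92–93% at 80%, and 78–81% (H1N1) / 75–78% (H3) at 50%. The loss comes from bias: at 50% typed, with subtypes drawn at random, the SD of the log ratio (0.068 / 0.074) equals the model SE. With half as many cases and 80% typed, coverage is 94–95% / 93–95%.

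**The case against.** The strongest reply is that the bias may never arise. The stated purpose of pooling is to learn which strains circulated, the 90% sentence is an example, and SAP 5.1.1.2 says missing data are not imputed. A reader might infer that imputed cases certainly enter the Cox models, but the documents do not say so. That use is inferred from the rule's place under the subtype-rVE objective and from the general Cox statement. This part stands, and it makes the point conditional. It also leaves two sections to reconcile, since 4.3 plainly describes imputation.

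Second, vaccinees are typed before unvaccinated cases, so the typed share may be high and the effect small. This also stands, but the plan does not secure it: only a proportion of outpatient specimens is typed, in one or perhaps two of three seasons.

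A reader might also infer from the power appendix that 0.00089/0.00218 = 41% of cases are inpatient and therefore untyped. That does not follow. Protocol 8.1.1 says very few cases are admitted, and SAP 4.2 counts admissions up to 14 days after a positive test, so some admitted patients may have an outpatient specimen.

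Nor do the documents support a claim that the rule creates false differences between subtypes. With true rVEs of 15% / 15%, a gap of 16.9% / 12.8% appears only if there is one typed unvaccinated case per SD-IIV case, 80% of them H1N1 against 50% in SD-IIV cases, and 85% of Flublok but 75% of SD-IIV cases are typed. With 80% and 78% typed it is 15.4% / 14.6%, and with equal shares it is zero.

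**Conclusion.** The point holds conditionally and is minor. SAP 4.3 describes an imputation that ignores vaccine received, SAP 5.1.1.2 excludes imputation, and the use of imputed cases in the rVE models is left open. If they are used, the true rVE differs by subtype and the typed shares are similar in the two arms, the subtype rVEs are pulled toward each other. At an assumed 0% / 30% and a 50:50 mix, the shift is 1 to 2 points at 90% typed, about 3 at 80% and 7 to 8 at 50%; at a 90:10 mix the minority subtype is off by about 5 points at 80%. A contrast of 10% / 30% gives smaller shifts. The true rVEs and typed shares are assumptions.

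It would be wrong to read this as a threat to the main results. The primary and secondary analyses, including influenza A and B separately, do not use subtype and are unaffected.

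**What to change.** In the SAP:

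1. Reconcile 4.3 with the no-imputation sentence in 5.1.1.2, and state whether imputed subtypes are used to estimate rVE.
2. Keep the pooled strain mix for describing circulation only.
3. If imputed subtypes are used for rVE, use multiple imputation conditional on vaccine arm, period and age group, with unvaccinated cases left out or given their own level, and Rubin's-rule variances. Restrict it to seasons with typing, and state the assumption needed for untyped inpatient cases. Single imputation within arm is not enough: in simulation it rejected a true null 5.9% to 16.7% of the time at a nominal 5%.
4. Add a typed-cases-only sensitivity analysis, and report the typed share by arm and period.

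The cost is wording and modest programming; no further specimens are needed. Against the pooled rule, the SE of the log rHR rises by about 3% / 3% (H1N1 / H3) at 90% typed, 6% / 7% at 80% and 22% / 27% at 50%. With a small contrast (10% / 30%) and 80% typed, the pooled rule has slightly lower RMSE (0.070–0.073 / 0.075–0.079 against 0.074 / 0.080). What the change buys is coverage close to nominal (about 95% at 50%, 80% and 90% typed, truth 0% / 30%) and no systematic pull, rather than a smaller RMSE in every case.

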5.1 Statistical Methods

5.1.1 Hypotheses and Statistical Methods for Primary, Secondary, and Exploratory Objectives

5.1.1.1 Hypotheses

For the primary objective, we plan to test the null hypothesis that there is no difference in effectiveness between Flublok and SD-IIV. We will use a 2-sided test ($p<0.05$) with an associated 95% confidence interval to assess superiority. The same null hypothesis of no difference in effectiveness will be tested for all secondary objectives. Analyses in subgroups defined by pre-existing conditions will not adjust for multiplicity; all other secondary analyses will adjust for multiplicity by the Holm method specified in Section 4.2.

5.1.1.2 Statistical Methods

The primary, secondary, and exploratory analyses will use Cox regression on a calendar timeline to obtain an adjusted estimate of the relative hazard ratio (rHR) for each outcome, adjusted for age, sex, race/ethnicity, and facility or service area. The null hypothesis (that the $\log rHR = 0$) will be tested using the Wald test (based on the ratio of the adjusted $\log rHR$ estimate to its corresponding standard error estimate). The following covariates have been selected *a priori* to include in our model (via the propensity score, described further below):

- Age at time of vaccination (continuous)
- Sex
- Race (some small categories may be combined, if necessary):
 - White
 - Black
 - Asian
 - Pacific Islander
 - Native American
 - Multiracial
 - Unknown/Other
- Ethnicity:

- Hispanic
- Non-Hispanic/Unknown
- KPNC Facility or Service Area

In addition to estimating the rHR, conditional on the covariates above, we will consider whether the rVE of Flublok varies across subgroups or over time. For example, we may examine whether the rHR varies with:

- Time-since-vaccination: number of days, counting from Day 15 after vaccination (where day 0 is the day of vaccination)
- Time-since-beginning-of-the-season
- Season: Year 1, Year 2, or Year 3
- Comorbidities: Diagnostic cost groups (DxCG) risk scores from the ICD-based proprietary risk adjustment and predictive modeling system may be used. DxCG calculates projected healthcare costs for each member for the upcoming year based on demographics, diagnoses, costs, and utilization in the previous year. It may also be included as a proxy for overall health status of the individual.
- Prior healthcare utilization (e.g., number of emergency department visits or hospitalizations in prior year, outpatient visits in prior year)
- Influenza vaccine type received (or none) during the previous year

Adults who are included in our analysis must receive either Flublok or an SD-IIV. The majority of influenza vaccinations are administered in the KPNC region by the end of calendar year. It is possible that Flublok will not last until the end of the influenza season, which is typically in the spring of the following year, as determined by KPNC. Based on our alternating weekly schedule—one week of Flublok followed by one week of an SD-IIV—weeks are “paired” for balance.

The following analyses will be conducted. The single-season analyses are for the purposes of assessing whether any season-specific considerations (or otherwise) need to be made for the overall analysis.

At the end of the third influenza season, we will assess:

- Single-season rVE against PCR-confirmed influenza (primary objective) based on data from the first influenza season (2018–2019)
- Single-season rVE against PCR-confirmed influenza (primary objective) based on data from the second influenza season (2019–2020)
- Single-season rVE against PCR-confirmed influenza (primary objective) based on data from the third influenza season (2020–2021)
- Potential single-season rVE against select secondary outcomes as feasible based on data from the first influenza season (2018–2019)

- Potential single-season rVE against select secondary outcomes as feasible based on data from the second influenza season (2019–2020)
- Potential single-season rVE against select secondary outcomes as feasible based on data from the third influenza season (2020–2021)

We expect that the featured analysis of rVE against each of the primary, secondary, and exploratory outcomes will be the overall analysis including all subgroups over both influenza seasons. If we find variation in rVE across subgroups and over time that is substantial, it will also be reported.

Risk sets will be conditioned (i.e., stratified) on calendar day, using a calendar timeline for the Cox regression. We expect many people to be vaccinated both years, and some might get “breakthrough” influenza both years. Getting Flublok in one year should be entirely unrelated to getting Flublok in another year, so robust standard errors are not needed. We will check our assumption that the vaccine received in one year is not related to vaccine received the next year. For each type of outcome, follow-up would end at the first outcome event in a season but could restart the next year when the individual is vaccinated again.

We do not know whether prior vaccination (i.e., booster or priming effect) affects VE of either Flublok Quadrivalent vaccine or SD-IIV, but we hypothesize that prior vaccination might be an effect modifier but not a potential confounder because what patients are vaccinated with in prior years should not be associated with what type of vaccine they receive in either of the 2 study seasons. We will test to ascertain if, as expected, there is (1) no correlation between prior vaccination (before the study period) and type of vaccination during the 3 study seasons, and (2) no correlation between the type of vaccine received in the one season and the type of vaccine received in the another study season. If we find that there is a relationship in any of these scenarios, we can treat prior vaccination (“prior” meaning before the study commenced, or “prior” as in vaccination in the first study season relative to the second study season) as a potential confounder. We would add variables that adjust for whether a patient was vaccinated during the past year(s), as well as which vaccine type they received. Further, if prior vaccination does modify VE, we may have adequate power to assess whether there is a boosting effect given our large sample size.

There is little possibility of confounding that may occur between patients tested versus those who are not tested. While not everyone with suspected influenza will be tested, the randomization process in vaccine supply (Flublok Quadrivalent vaccine versus SD-IIV) should result in an equal distribution of those who are and are not tested between the two vaccine groups throughout the season. We will attempt to mitigate possible bias and confounding as much as possible upfront by implementing our plans for supplying clinics with alternating shipments of vaccines. Because factors related to testing should be balanced, there is no reason to believe that the likelihood of being tested (conditional on influenza infection and severity) will be related to whether a person received Flublok Quadrivalent vaccine or SD-IIV. (It may be helpful to compare the RSV results of Flublok vs. SD-IIV vaccinees to assess our assumption of no residual confounding.)

We will also be monitoring the balance of potential confounders that may be related to influenza and to PCR testing in order to confirm that we are achieving the balance intended by our quasi-randomized shipment of vaccines to clinics. Once vaccinations begin, we will monitor on a weekly basis the balance of Flublok vaccinees versus SD-IIV vaccinees with respect to facility,

sex, and age group (18–49 years and 50–64 years). Additional demographic variables such as race and ethnicity may also be monitored. We will also monitor balance with respect to comorbidities such as chronic obstructive pulmonary disease (COPD), asthma, and diabetes. If we find that any facility is using Flublok or SD-IIV more (or less) than needed to achieve balance, we will work with the influenza program manager to adjust what is being administered.

By design, inpatient facilities did not participate in the quasi-randomization of influenza vaccine administration. We will therefore exclude patients who received Flublok or SD-IIV during an inpatient stay as these may be higher risk. Facilities that used only Flublok or only SD-IIV will also be excluded from the analysis.

In preparing our dataset for analysis, we will assess the balance in several ways to determine if the imbalance is substantially more than what we would expect to see. Despite our efforts, we anticipate that there will still be imbalances. We will create a facility-specific propensity score for each vaccinee, scoring their probability of receiving Flublok versus SD-IIV as a function of covariates, including but not limited to age, sex, race, ethnicity, comorbidity scores, influenza vaccination, and prior healthcare utilization history. Our Cox regression will be adjusted for the propensity score.

For PCR-confirmed outcomes, we plan to assess the outcomes that occur ≥ 14 days after vaccination up through to the end of each influenza season (as determined by KPNC, which is generally when the proportion of influenza-positive PCR tests drops below 10%) or the first week of May, whichever is later. For outcomes that are not tied to PCR-confirmation, the outcome or diagnosis must occur on or after the first day that KPNC begins use of the Cepheid GeneXpert PCR assay for the influenza season (generally the first Tuesday of October), but must begin no later than 14 days after the last day of the influenza season, as determined by KPNC.

It is possible that patients enter, exit, and re-enter the KPNC population during the study period. Only patients who are members at the time of vaccination will be included in the analysis in order to most accurately ascertain the vaccine received. If additional exclusions need to be made based on membership, we will make the most appropriate determination for how to handle such cases at the analysis stage, but we anticipate that this would be a very small number of patients. Missing data will not be imputed.

For outcomes not based on PCR-confirmed influenza (e.g., hospitalized pneumonia and cardio-respiratory events), we will include in the analysis all such outcomes occurring within 14 days after the last day of the influenza season (as determined by KPNC) to account for influenza that may still be circulating after the “official” end of the season.

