11.1 Statistical Methods

Since we are not randomizing at the individual patient level, there is no vaccine being assigned to any patient. The intent is to balance Flublok versus SD-IIV comparisons by balancing the shipments and delivery of the vaccines by clinic and calendar week.

The preliminary analyses will compare the incidence of each of the outcomes in Flublok Quadrivalent vaccinees versus SD-IIV vaccinees. We plan to test the null hypothesis that Flublok is not any more effective than the comparator (i.e., a superiority test), using a 2-sided test, $p<0.05$. The primary analyses will use Cox regression to obtain an adjusted estimate of the relative hazard ratio (rHR) for each outcome, adjusted for age, sex, race/ethnicity, facility, and time-since-vaccination. The rHR at any point in the follow-up period is the instantaneous relative risk (RR) at that time (i.e., we are estimating rVE by $(1-rHR)$, and testing the null hypothesis that $rHR=0$). In addition, we may adjust for an available comorbidity score and/or a measure of prior exposure to influenza vaccines (e.g., exposure to flu vaccine in the prior year, or number of flu shots in the past three years).

Risk sets will be conditioned (i.e., stratified) on calendar day, using a calendar timeline for the Cox regression. We expect many people to be vaccinated both years, and some might get “breakthrough” influenza both years. Getting Flublok in one year should be entirely unrelated to getting Flublok in another year, so robust standard errors are not needed. We will check our assumption that the vaccine received in one year is not related to vaccine received the next year. For each type of outcome, follow-up would end at the first outcome event in a season but could restart the next year when the individual is vaccinated again.

We do not know whether prior vaccination (i.e., booster or priming effect) affects VE of either Flublok Quadrivalent vaccine or SD-IIV, but we hypothesize that prior vaccination might be an effect modifier but not a potential confounder because what patients are vaccinated with in prior years should not be associated with what vaccine they receive in any of the 3 study seasons. We

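### The SAP drops the protocol's time-since-vaccination adjustment from the primary Cox model and sets no rule for SD-IIV-only weeks, so vaccination date is uncontrolled if Flublok runs out

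*SAP*

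**What the plan says.** Protocol 11.1 describes the primary Cox analyses as "adjusted for age, sex, race/ethnicity, facility, and time-since-vaccination". The design aim in the same section is comparability through "balancing the shipments and delivery of the vaccines by clinic and calendar week".

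The model sentence in SAP 5.1.1.2 lists age, sex, race/ethnicity and facility or service area. Its a priori covariate list adds nothing on timing. Time since vaccination appears only in a later list introduced by "we may examine whether the rHR varies with", which is optional and concerns effect modification.

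On supply, the same SAP section says "It is possible that Flublok will not last until the end of the influenza season". It then describes the schedule as "one week of Flublok followed by one week of an SD-IIV" and treats weeks as paired for balance. It does not say what happens to a week without a pair.

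Other provisions that bear on this:
- "Risk sets will be conditioned (i.e., stratified) on calendar day" (SAP 5.1.1.2).
- Facilities that used only one product are excluded. The Cox model is adjusted for a facility-specific propensity score whose covariate list is open-ended but names no vaccination date or week (SAP 5.1.1.2).
- Single-season analyses serve the purpose of "assessing whether any season-specific considerations (or otherwise) need to be made for the overall analysis", and before analysis "we will assess the balance in several ways to determine if the imbalance is substantially more than what we would expect to see" (SAP 5.1.1.2).
- Protocol 11.1 permits, but does not require, adjusting for or stratifying by relevant covariates if imbalance remains.

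**The concern.** The two documents specify different primary models. The dropped term is the one that matters in a situation the SAP itself foresees. If Flublok is exhausted before SD-IIV, everyone vaccinated afterwards is in the SD-IIV arm, and that arm has, on average, later vaccination dates.

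Two paths lead from there to a biased rVE:
- **Waning.** If protection declines, recently vaccinated SD-IIV recipients have lower hazard on a given day, and Flublok looks worse than it is.
- **Baseline risk.** If late vaccinees differ from early ones in ways the propensity score does not capture, the bias can go either way.

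As written, the handling of SD-IIV-only weeks would be chosen after the data are seen.

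**Working it through.** **1. Do the existing provisions control vaccination date?**
- Risk sets: on calendar day t, a person vaccinated on day v has time since vaccination t − v. The risk set fixes t but not v, so people compared on one day still differ in vaccination date. Because t is constant within a risk set, a linear time-since-vaccination term is equivalent to a linear vaccination-date term.
- Facility exclusion: it acts on whole facilities. One that alternated and then ran out stays in.
- Propensity score: no vaccination date is named.
- Balance checks and single-season analyses: they can detect the problem but do not commit to an analysis.

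**2. The plan's own power figure.** Protocol appendix, row 28 (ages 50-64, PCR-confirmed influenza): 519,699 per arm, comparator proportion 0.00205, RR 0.85.
- Events: 519,699 × 0.00205 = 1,065; × 0.85 = 906.
- SE(log rHR) = √(1/906 + 1/1,065) = 0.0452.
- Power = Φ(0.1625/0.0452 − 1.96) = 0.949. The protocol states 0.95.

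**3. Size of the bias.** The documents give no run-out date, late share or waning rate, so these are assumptions. The late shares of 8% and 25% are illustrative. They imply 800,000 × 0.92/2 = 368,000 and 800,000 × 0.75/2 = 300,000 Flublok doses per season, against about 400,000 planned (protocol 5.1.4).

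*Hand check.* Allocation is 1:1 until run-out and SD-IIV only after. Late share of the SD-IIV arm = L/[(1 − L)/2 + L], which is 0.08/0.54 = 14.8% or 0.25/0.625 = 40%. Take waning of 10% per 28 days and late vaccinees 8 weeks more recent, so their relative hazard is 1/1.1² = 0.826.
- 25% late: SD-IIV mean hazard 0.6 + 0.4 × 0.826 = 0.931; rHR 0.85/0.931 = 0.913 in the affected season. Averaging logs over three seasons with one affected: (2 ln 0.85 + ln 0.913)/3 = −0.139, so rVE reads about 12.9%.
- 8% late: 0.852 + 0.148 × 0.826 = 0.974; rHR 0.872; average log −0.154, so rVE reads about 14.3%.

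*Fuller model.* Expected-value Cox model on weekly risk sets:
- 75% of vaccinations evenly over 10 weeks to Thanksgiving, 25% in a geometric tail over 22 weeks (weekly ratio 0.80-0.95);
- follow-up from 2 weeks after vaccination;
- epidemic peak at week 16, 20 or 24 from mid-September, SD 4 weeks;
- three equally weighted seasons, true rVE 15%.

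| Run-out | Late | Waning 5-15% per 28 days | Power | Late-vaccinee residual HR 0.8-1.2 |
|---|---|---|---|---|
| none | – | 15.0% | 0.95 | – |
| 1 of 3 seasons | 8% | 13.8-15.0% | 0.91-0.95 | 14.3-15.7% |
| 1 of 3 seasons | 25% | 11.9-14.5% | 0.80-0.93 | 12.9-17.0% |
| all 3 seasons | 8% | 11.3-15.0% | 0.76-0.95 | 12.9-17.0% |
| all 3 seasons | 25% | 5.1-13.5% | 0.21-0.89 | 8.0-21.0% |

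With run-out on 31 December and 1-2% vaccinated later, the waning reading is 14.1-15.0%.

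**4. Does the protocol's term repair it?** Linear time since vaccination returns 15.0% under waning in every case run. With a residual hazard ratio of 0.8-1.2 and 25% late, it leaves 13.3-16.6% (one season) or 12.1-17.6% (all three).

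**The case against.** The strongest case against is that the bias needs two things the documents do not establish: run-out, and hazard that differs by vaccination date. Supply is planned at 1:1. The SAP's warning is about lasting to the end of the season, typically spring, and follows the remark that most vaccinations are given by the end of the calendar year. That does not suggest exhaustion at Thanksgiving. Protocol 5.1.4 puts more than 75% of vaccinations before Thanksgiving, so 25% late is a ceiling for a run-out then. The open propensity list, the balance checks and the protocol's permissive clause would all allow a correction. On the baseline-risk path, the SAP's propensity score may protect better than the protocol's optional comorbidity adjustment.

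All of this stands, and it limits the size. It does not close the gap. The SAP raises run-out itself, the available corrections are discretionary, and the protocol had already committed to the relevant covariate.

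Three stronger readings are not supported:
- *The primary rVE is biased.* Nothing shows that Flublok ran out.
- *rVE could collapse to about 5%, or Flublok could be falsely declared superior.* The low reading needs 25% late in all three seasons with strong waning. False superiority of 12-39% (nominal 2.5%) needs 25% late in all three seasons plus a hazard ratio of 1.2 left after propensity adjustment, a value with no support in the documents.
- *The change was concealed because SAP 5.5 does not list it.* That section points to protocol amendments, and its silence alone proves little.

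**Conclusion.** The concern holds as a conditional one. The protocol and SAP disagree on a primary-model covariate without explanation, and no committed SAP provision controls vaccination date if Flublok runs out. If alternation holds all season there is no such bias.

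If run-out affects one season, assumed waning of 5-15% per 28 days moves a true 15% to about 13.8-15.0% (8% late) or 11.9-14.5% (25% late). A late run-out with few later vaccinees has little effect. Larger distortions require early run-out in all three seasons, which is an extreme case. Waning biases against Flublok; residual baseline risk may act in either direction. All sizes rest on assumed uptake, epidemic timing, late share and waning.

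**What to change.** **Primary model.** Restore time since vaccination, or vaccination week, in the SAP primary Cox model as in protocol 11.1, or explain its removal. Put it in the outcome model. A flexible date term in the facility-specific propensity score would be a poor substitute: under weekly alternation, week nearly determines product within a facility, so scores would move towards 0 or 1 and overlap would be lost.

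**SD-IIV-only weeks.** State before analysis how people vaccinated in those weeks are handled.

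**Cost.** SAP wording and programming on data already recorded, plus a small loss of precision. In a separate grouped model with 5%, 11% or 22% of doses late, the standard error rose from about 0.042-0.045 to 0.042-0.049.

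**Sensitivity analysis.** Stratify by facility and paired two-week vaccination period within season, defined from recorded product and date. Single-product strata then drop out of the contrast. In the cases run this read 15.0% under waning and 14.7-15.3% at residual hazard ratios of 0.8-1.2. It is better as a sensitivity analysis than as the primary model, for these reasons:
- The effective population is narrower than the all-vaccinee population of SAP 2.1.
- Clean pairs are not assured. Protocol 5.1.3 and 5.1.4 let supply alternate by delivery, vary with usage, and sometimes leave both vaccines in a clinic.
- Power at rVE 15% falls from 0.95 to about 0.93, 0.91 or 0.88 if 8%, 15% or 25% of vaccinees sit in single-product strata (events 833 v 980, 770 v 906, 679 v 799).
- Strata are thin. With 70 facilities, 16 periods and 3 seasons there are 3,360. The 1,050 before Thanksgiving hold about 742 vaccinees each (0.75 × 1,039,398/1,050), and the 2,310 later ones about 112. At 1,971/1,039,398 events per vaccinee, that is about 1.4 and 0.2 events per stratum.
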